### SAP and protocol version

SAP version and date	Version 1.0, 07.11.2024
Protocol version	App-Delivered Cognitive-Behavioral Therapy for Insomnia Among Patients   NSS (dovepress.com)

### SAP revision history

Protocol version	SAP version	Date changed	Description and reason for change

**STATISTICAL ANALYSIS PLAN for “Digital sleep therapy in patients with Musculoskeletal complaints and insomnia”**

## **Abbreviations**

SAP	Statistical Analysis Plan
CBT-I	Cognitive-behavioral therapy for insomnia
DCBT-I	Digital versions of CBT-I
RCT	Randomized clinical trial
ISI	Insomnia Severity Index
NPD	Norwegian Prescription Database
NAV	National Insurance Administration
HSCL-25	Hopkins Symptom Checklist, 25 questions
EQ-5D	European Quality of Life – 5 Dimensions
PSFS	Patient Specific Functional Scale
ITT	Intention to treat
SD	Standard deviation
IQR	Interquartile range
OR	Odds ratio
HUNT3 PA	Trøndelag Health Study (HUNT Study), physical activity questionnaire

## STATISTICAL ANALYSIS PLAN for “Digital sleep therapy in patients with Musculoskeletal complaints and insomnia”

### 1. Introduction

This Statistical Analysis Plan (SAP) should be read in conjunction with the published trial protocol: *App-Delivered Cognitive-Behavioral Therapy for Insomnia Among Patients with Comorbid Musculoskeletal Complaints and Insomnia Referred to 4-Week Inpatient Multimodal Rehabilitation: Protocol for a Randomized Clinical Trial* [1]. The information available here provides a more detailed description of the “Statistical analysis” section.

#### 1.1 Purpose and scope of the statistical analysis plan

This document details the proposed analyses of the main paper reporting results from the study *“Digital sleep therapy in patients with musculoskeletal complaints and insomnia referred to inpatient multimodal pain rehabilitation”*. Any deviations from the analyses outlined in this SAP will be described and justified in the final report of the trial, including the inclusion of any analyses suggested by journal editors and referees. Modifications will be carefully considered and, as far as possible, follow the broad principles set out here.

First and foremost, this SAP describes the analysis of the primary and secondary outcomes. Subsequent exploratory analyses are also expected to follow the broad principles of this SAP but are not described in detail here.

The details presented here shall not prohibit accepted practices, such as data transformation prior to analysis. When possible, such data management and modelling decisions will be undertaken prior to revealing the treatment allocation. The final analysis strategy will be available on request when the papers are submitted.

#### 1.2 Background and rationale

Insomnia is prevalent among patients receiving treatment for long-term musculoskeletal complaints in inpatient rehabilitation settings. Cognitive-behavioral therapy for insomnia (CBT-I) is effective for improving sleep quality in patients with pain, but a lack of therapists often limits the capacity to use this therapy in rehabilitation programs. To increase the availability of CBT-I, self-guided, fully automated digital versions of CBT-I (dCBT-I) have been developed. An advantage of dCBT-I is that it can be an add-on to usual care. The aim of this randomized clinical trial (RCT) is to evaluate the effectiveness of app-delivered dCBT-I adjunct to inpatient multimodal rehabilitation for individuals with comorbid musculoskeletal complaints and insomnia, compared with rehabilitation (usual care) only.

#### 1.3 Objectives

##### 1.3.1 Primary objective

The primary objective of this trial is to evaluate the effectiveness of dCBT-I on insomnia severity for patients with long-term musculoskeletal complaints in inpatient multidisciplinary rehabilitation compared to inpatient multidisciplinary rehabilitation only during 12 months of follow-up. The main assessment point will be 3 months after end of rehabilitation.

### **1.3.2 Secondary and exploratory objectives**

Secondary objectives:

- 1) Examine the difference in the proportion of participants that achieves an 8-point improvement in their ISI-score between inpatient multidisciplinary rehabilitation + dCBT-I (intervention group) and inpatient multidisciplinary rehabilitation only (control group), 3-, 6-, and 12 months after end of rehabilitation.
- 2) Evaluate the effectiveness of the intervention on pain intensity, fatigue, health-related quality of life, physical function, and physical activity at 3-, 6-, and 12 months after end of rehabilitation.
- 3) Evaluate the long-term effectiveness of the intervention on sickness absence and use of prescribed sleep and pain medication during 12 months of follow-up after rehabilitation (this will be done if successful register linkage within the time frame of the project).

If the data material allows it, it will be relevant to examine the following exploratory objectives:

- 4) Explore whether changes in pain intensity and fatigue mediate the effect of dCBT-I on insomnia severity.
- 5) Explore whether sex, age, symptoms of anxiety and depression, pain intensity and level of physical activity at baseline moderate the effect of dCBT-I on insomnia severity and secondary outcomes (pain intensity, health-related quality of life, sickness absence and use of prescription sleep and pain medication).

## **2. Study design**

### **2.1 Study design**

The trial is as a cluster-randomized clinical trial with two parallel groups, investigating the effects of dCBT-I on insomnia symptoms for patients with comorbid musculoskeletal complaints and insomnia in inpatient rehabilitation compared with traditional inpatient rehabilitation only (figure 1). To maximize the number of participants receiving the additional treatment (dCBT-I), the participants are randomized to the intervention and usual care at a ratio of 2:1.

### **2.2 Randomization and treatment assignment**

The randomization will be at group level to avoid contamination between members of the same rehabilitation group. Each group are randomized using a computer-generated block randomization provided by the Clinical Research Unit (Project support) at the Faculty of Medicine and Health Sciences at the Norwegian University of Science and Technology (third party).

## STATISTICAL ANALYSIS PLAN for “Digital sleep therapy in patients with Musculoskeletal complaints and insomnia”

[figure not shown]

Figure 1 Flow of participants in the study

### 2.3 Determination of sample size

We anticipated that around five of 10 patients will have insomnia within each rehabilitation group and that the average Insomnia Severity Index (ISI)-score for participants completing usual treatment will be 15 ( $SD = 4$ ). An average 4-point improvement on the ISI score is considered a meaningful change. In order to maximize the number of participants receiving the additional treatment (dCBT-I), we will randomize the participants to the intervention and usual care at a ratio of 2:1. Recruiting 15 clusters with 2:1 randomization will achieve 80% power to detect a 4-point difference between the intervention and usual treatment group, with a conservative assumption that the intraclass correlation is 0.2 and the coefficient of variation in cluster size up to 0.7, and with a significance level of 5%. This would mean that around 150 participants will be screened to give an expected sample size of 75 (50 in dCBT-I + usual care and 25 in usual care). We expect a dropout rate of approximately 20% and that around 50% of the participants in the intervention group will complete at least four of the dCBT-I modules. Given that the per-protocol analysis is of particular interest in this study, we aim to recruit 21 clusters to account for the fact that we expect an average of four participants per cluster in the control group to complete the follow-up, and an average of two participants in the intervention group to complete at least four of the modules and attend the follow-up.

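### The 80% power stated for 15 clusters rests on a large-sample reference distribution; on cluster-level degrees of freedom it is about 70–75% at the plan's own cluster-size limit, while the 21-cluster target remains adequate for ITT

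*SAP*

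**What the plan says.** SAP section 2.3 expects that "around five of 10 patients will have insomnia within each rehabilitation group". It takes an SD of 4 on the ISI, a 4-point difference, an ICC of 0.2 described as conservative, a cluster-size CV of up to 0.7 and a 5% level, and concludes: "Recruiting 15 clusters with 2:1 randomization will achieve 80% power to detect a 4-point difference between the intervention and usual treatment group". That corresponds to 75 participants, 50 and 25. Section 2.4 makes the tests two-sided. No test, formula or degrees of freedom is named for the calculation.

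The same paragraph then says "We expect a dropout rate of approximately 20" per cent and expects about half of the intervention arm to complete at least four modules. Because the per-protocol analysis is of special interest, it continues "we aim to recruit 21 clusters". This is based on averages of four control participants per cluster at follow-up, and two intervention participants per cluster who both reach module four and attend follow-up. No power is given for 21 clusters.

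Section 2.2 randomises by rehabilitation group. The primary model in section 5.2 has a random effect for participant only. Section 5.2.1 adds rehabilitation group as a third level in a sensitivity analysis and names no small-sample degrees of freedom.

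**The concern.** With 15 groups split 10 to 5, the between-arm contrast has about 15 − 2 = 13 degrees of freedom, however many participants each group holds. A cut-off of 1.96 is then too small. Referred to t on 13 df, it has a two-sided level of about 7.2%. A power figure obtained with that cut-off is therefore not the power of a 5% test, yet section 2.3 states 80% and 5% together.

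The only power figure in the SAP also belongs to a design that is not the recruitment target. A reader cannot see what 21 clusters deliver for either analysis, and may take 15 as already sufficient. In the three-level model, a z reference with 15 to 21 groups would likewise make intervals too narrow.

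**Working it through.** **Inputs** (SAP sections 2.3 and 2.4): difference 4; SD 4; ICC ρ = 0.2; CV = 0.7; mean cluster size m = 5, or 4 after 20% dropout; 10 v 5 clusters (15) or 14 v 7 (21); two-sided 5%.

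**Formulas.** SE = SD × √[DE × (1/n₁ + 1/n₂)]. Two standard design effects (DE) allow for unequal cluster sizes:
- Form A (relative efficiency): DE = [1 + (m−1)ρ] / [1 − CV²·L(1−L)], with L = mρ/(mρ + 1 − ρ).
- Form B: DE = 1 + [(1 + CV²)m − 1]ρ.

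Power is taken from the normal distribution with cut-off 1.96, or from the noncentral t with (clusters − 2) df. The t cut-offs are 2.160 on 13 df and 2.093 on 19 df.

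**Step 1: reproduce the plan's 80%.**
- Form A: L = 1/1.8 = 0.556, so L(1−L) = 0.247. DE = 1.8/(1 − 0.49 × 0.247) = 2.048. SE = 4√[2.048 × (1/50 + 1/25)] = 1.402, and 4/1.402 = 2.853. Power is 81.4% with z and 80.4% with t on 75 − 2 = 73 participant df. The plan's figure is reproduced.
- Form B: DE = 1 + (1.49 × 5 − 1) × 0.2 = 2.29, SE = 1.483, 4/SE = 2.698. Power with z is 77.0%, so this form does not reproduce it.

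**Step 2: cluster-level degrees of freedom, and the actual target (all at CV 0.7).**

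| Setting | Form | DE | SE | 4/SE | z | t, cluster df |
|---|---|---|---|---|---|---|
| 15 clusters, m = 5 | A | 2.048 | 1.402 | 2.853 | 81.4% | **75.1%** |
| | B | 2.290 | 1.483 | 2.698 | 77.0% | **70.4%** |
| 15 clusters, m = 4 | A | 1.823 | 1.479 | 2.704 | 77.2% | 70.6% |
| | B | 1.992 | 1.546 | 2.587 | 73.5% | 66.8% |
| 21 clusters, m = 4 (ITT) | A | 1.823 | 1.250 | 3.200 | 89.2% | **85.9%** |
| | B | 1.992 | 1.307 | 3.061 | 86.5% | **82.7%** |
| 21 clusters, 2 v 4 per cluster | A | 1.347 / 1.823 | 1.346 | 2.972 | 84.4% | **80.5%** |
| | B | 1.396 / 1.992 | 1.391 | 2.875 | 82.0% | **77.8%** |

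The last setting sets module completers against controls, with 14 × 2 = 28 and 7 × 4 = 28 participants, so SE = 4√(DE₁/28 + DE₂/28). That is the comparison implied by the counts in section 2.3; section 3.3.2 describes the per-protocol question as completers against non-completers.

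**Step 3: dependence on cluster-size variation** (15 clusters, m = 5, 13 df). At CV 0, DE = 1.8, SE = 1.315 and power is 80.3%. At CV 0.3 it is 79.4% (A) or 78.4% (B). With equal sizes but 20% dropout (m = 4, DE = 1.6, SE = 1.386) it is 76.1%.

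**Step 4: simulation** (15 clusters, m = 5, CV 0.7, 4,000 runs, Monte Carlo error about 0.7 points or less).

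| Analysis | Power | Type I error |
|---|---|---|
| Random-intercept REML, z | 80.0% | 7.7% |
| Random-intercept REML, t on 13 df | 74.9% | 5.6% |
| t-test on cluster means | 69.5% | 5.0% |

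**The case against.** Four stronger readings are tempting, and the document supports none of them.

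- **That the 80% is a calculation error.** It is not. It follows from the plan's own inputs by a standard method. What is at issue is the reference distribution.
- **That it holds only with a z-test.** That is too strong: t on 73 participant df gives 80.4%, and t on 13 df gives 80.3% with equal clusters. The first counts participants where clusters were randomised, so it shares the weakness. The second is genuine, but the plan claims 80% for CV up to 0.7.
- **That dropout was forgotten.** The 15-cluster sentence precedes attrition. The same paragraph then brings in dropout and adherence and moves to 21 clusters.
- **That the trial is underpowered.** At 21 clusters after dropout, ITT power is above 80% under either design effect. The SAP nowhere makes 15 a recruitment target or stopping point.

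Two further arguments qualify the size. The plan calls its ICC conservative and section 5.2.1 does not expect strong cluster effects; at ICC 0.1 and CV 0.7, power on 13 df would be 83.7–85.1%. The calculation also ignores any gain from baseline ISI. If that correlated 0.5 with follow-up at both levels and were used in the model, power at 15 clusters would be 82–86% before dropout; at 0.3 it would be 74–79%. The SAP gives no such correlation, so these are assumptions. They show that 70–75% is conditional on the stated inputs, but they do not restore the claim as written for ICC 0.2 and CV up to 0.7.

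The REML test on 13 df is also only approximately at 5% in simulation (5.6%), so the upper end of the range is slightly generous.

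**Conclusion.** The point holds as a correction to the stated figure. At ICC 0.2 and CV 0.7, 80% power and a 5% level do not hold together for 10 v 5 clusters. Power on cluster-level degrees of freedom is about 70–75% before dropout, some 5 to 10 points below the claim. The 21-cluster target gives about 83–86% for ITT after dropout. For completers against controls it is 77.8–80.5%, so the comparison that motivated the larger target sits at the margin.

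These figures assume exact 10:5 and 14:7 splits, dropout spread evenly over clusters, a single unadjusted follow-up comparison, and the plan's SD and ICC. No change to the design follows from them.

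**What to change.** 1. In section 2.3, name the test and degrees of freedom behind the power figure. Then either restate the 15-cluster power as about 70–75% at CV 0.7 before dropout on cluster-level df, or limit the 80% to roughly equal cluster sizes.
2. In the same section, add power at the 21-cluster target: about 83–86% for ITT after 20% dropout, and 77.8–80.5% for module completers against controls, with the assumptions stated.
3. In section 5.2.1, specify Kenward-Roger or Satterthwaite degrees of freedom for the treatment effect in the model that includes rehabilitation group.

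The cost is a revision of SAP wording, a less favourable 15-cluster figure, and slightly wider intervals in the three-level model. Recruitment is unaffected.

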### 2.4 Framework

The trial aims to test if dCBT-I is superior to usual care. Two-sided tests will be used for both primary and secondary objectives.

## **2.5 Statistical interim analyses and stopping guidance**

Since the participants receive medical supervision during the 4-week rehabilitation, we do not plan any interim analyses.

## **2.6 Timing of final analysis**

The main analyses will be performed at 12 months after end of rehabilitation. The primary outcome measure point is 3 months of follow-up. Results for 6- and 12 months of follow-up will be presented in the same publication.

## **2.7 Data sources and timing of endpoint assessments**

### **2.7.1 Data sources**

In the project we will use questionnaire and registry data. For the main outcome, questionnaire data will be used.

#### **Questionnaires**

Self-reported web-based questionnaires are answered at five time points: at baseline (prior to randomization), 6 weeks (at the end of rehabilitation), at 3 months (primary outcome measurement), 6 months, and 12 months after end of rehabilitation.

In addition, diagnoses and use of medication at baseline will be available through the electronic patient records.

#### **Registry Data**

Registry-based data will be obtained for 12 months of follow-up after rehabilitation from the Norwegian Prescription Database (NPD) and the National Insurance Administration (NAV). From NPD, we will obtain data on use of sleep and pain medications and assess the proportion of participants that obtain prescriptions of these medications during the follow-up. From NAV, we will obtain data on use of medical benefits (sick leave, work assessment allowance and disability pensions). Work participation outcomes will include both total number of days of sickness absence during 12 months follow-up and the probability of being at work (i.e., without medical benefits) each month during the same period.

**STATISTICAL ANALYSIS PLAN for “Digital sleep therapy in patients with Musculoskeletal complaints and insomnia”**

**2.7.2 Timing of endpoint assessments**

Table 1. Schedule for assessments

	Study period				
	Enrolment	Post-rehabilitation			
TIMEPOINT	Baseline	End of rehabilitation	3 months	6 months	12 months
ASSESSMENTS:					
Age					
Sex					
Education					
Work status					
Work satisfaction	X				
Work ability					
Work expectations					
Sleep and pain medication (from journal)					
Anxiety and depression (HSCL-25)	X	X			
Primary outcome					
Insomnia severity index (ISI)	X	X	X	X	X
Secondary outcomes					
Pain intensity	X	X	X	X	X
Fatigue	X	X	X	X	X
Health-related quality of life (EQ-5D)	X	X	X	X	X
Physical function (PSFS)	X	X	X	X	X
Physical activity (HUNT3 PA)	X		X	X	X
Registry data					
Sickness absence and disability pension					→
Sleep and pain medication					

HSCL-25: Hopkins Symptom Checklist, 25 questions. EQ-5D: European Quality of Life – 5 Dimensions. PSFS: Patient Specific Functional Scale. HUNT3 PA: Trøndelag Health Study (HUNT Study), physical activity questionnaire.

### **3. Statistical principles**

#### **3.1 Confidence intervals and p-values**

We will use two-sided tests and report mean differences with 95% confidence intervals.

#### **3.2 Adherence, protocol deviations and protocol violations**

Adherence will be defined as completing at least the 4 first modules of dCBT-I as stimulus control is in module 4.

### **3.3 Analysis populations**

#### **3.3.1 Intention to Treat (or Full Analysis Set)**

Effect analyses of primary and secondary outcomes will be performed after the intention-to-treat (ITT) principle, i.e., we will include all participants that were included and randomized.

#### **3.3.2 Per-Protocol Analysis Set**

Per-protocol analyses will be performed for individuals who complete  $\geq 4$  dCBT-I modules to explore whether patients who complete  $\geq 4$  dCBT-I modules have a greater effect on insomnia severity 3 months after intervention than patients who complete  $< 4$  dCBT-I modules.

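### The per-protocol comparator is inconsistent: SAP 2.3 sizes the trial on completers and followed-up controls, while SAP 3.3.2 names only patients with fewer than four modules, a self-selected comparison

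*SAP*

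**What the plan says.** SAP 2.3 first justifies 15 clusters: "Recruiting 15 clusters with 2:1 randomization will achieve 80% power to detect a 4-point difference". It then enlarges the trial for a different purpose: "Given that the per-protocol analysis is of particular interest in this study, we aim to recruit 21 clusters". The reason given is a pair of expected counts per cluster. For usual care the figure is "an average of four participants per cluster in the control group to complete the follow-up". For the dCBT-I arm the figure is lower, because module completion is required as well as follow-up: "an average of two participants in the intervention group to complete at least four of the modules and attend the follow-up". Intervention patients who complete fewer than four modules are not counted.

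SAP 3.2 sets the adherence threshold: "Adherence will be defined as completing at least the 4 first modules of dCBT-I". SAP 3.3.2 then defines the per-protocol analysis. It is done for those with at least four modules, in order to explore whether they "have a greater effect on insomnia severity 3 months after intervention than patients who complete" fewer than four. The control arm does not appear in that section.

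SAP 5.2 to 5.4 give no per-protocol model, comparator or adjustment. For the main analyses SAP 3.3.1 is clear: "Effect analyses of primary and secondary outcomes will be performed after the intention-to-treat (ITT) principle".

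**The concern.** The two sections describe different comparisons. The counts in 2.3 belong to completers versus usual care. The wording of 3.3.2 most naturally means completers versus non-completers within the intervention arm, although it does not literally say so.

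Completing four modules is something patients do after randomisation. Those who persist may differ from those who stop in motivation, severity or prognosis, so a difference between them mixes any effect of the app with those differences. Because 3.3.2 speaks of a greater effect, such a difference could be reported as a benefit of completing the programme.

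An analyst who follows 3.3.2 could also run a contrast other than the one for which 21 clusters were chosen. The control clusters added by the enlargement would contribute nothing to a comparison made wholly within the intervention arm.

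**Working it through.** **Inputs, all from SAP 2.3 and 2.4.** Difference 4 points, SD 4, intraclass correlation (ICC) 0.2, coefficient of variation of cluster size (CV) up to 0.7 (0.7 used), two-sided 5%, 2:1 allocation, about 5 eligible patients per cluster, 20% dropout, 50% of the intervention arm completing at least four modules.

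**1. The plan's own figure.** Two standard allowances for unequal clusters of mean size m were used:

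- Form A: design effect = 1 + ((CV² + 1)m − 1) × ICC.
- Form B: design effect = [1 + (m − 1) × ICC] / [1 − CV² × L(1 − L)], with L = m × ICC / (m × ICC + 1 − ICC).

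For 10 v 5 clusters of 5 (50 v 25 patients), form B gives L = 0.556 and a design effect of 1.8/0.879 = 2.05. Then SE = √[16 × 2.05 × (1/50 + 1/25)] = 1.40, and power = Φ(4/1.40 − 1.96) = 81.4%. Form A gives 77.0%. The stated 80% is reproduced.

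**2. The counts in 2.3.**

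- Controls per cluster: 5 × 0.8 = 4.
- Completers per cluster: 5 × 0.8 × 0.5 = 2.
- 21 clusters (14 + 7): 14 × 2 = 28 completers and 7 × 4 = 28 controls.
- 15 clusters (10 + 5): 20 completers and 20 controls.
- Moving to 21 adds 2 control clusters, that is 2 × 4 = 8 controls.
- Followed-up non-completers at 21 clusters: 14 × 4 − 28 = 28. Section 2.3 does not use this group.

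**3. Power for completers versus controls, 4 points.** Form A design effects are 1.396 (m = 2) and 1.992 (m = 4); form B gives 1.347 and 1.823. SE = √[16 × (DE₁/n₁ + DE₀/n₀)].

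| Clusters | n | SE (A / B) | Power, normal (A / B) | Power, t (A / B) |
|---|---|---|---|---|
| 21 | 28 v 28 | 1.391 / 1.346 | 82.0% / 84.4% | 77.8% / 80.5% (19 df) |
| 15 | 20 v 20 | 1.646 / 1.592 | 68.1% / 70.9% | 61.3% / 64.2% (13 df) |

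The step from 15 to 21 clusters brings this contrast back to about 80%. The SAP states no power for ≥4 versus <4 modules.

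**4. Selection, for illustration only.** Assume no true effect, SD 4, 50% completion, and a normal underlying adherence score correlated r with prognosis. The SAP gives no r.

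- Completers versus non-completers: 2 × √(2/π) × r × 4 = 0.64, 1.28, 1.91, 2.55 points for r = 0.1, 0.2, 0.3, 0.4.
- Completers versus controls: √(2/π) × r × 4 = 0.32, 0.64, 0.96, 1.28 points.

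The second contrast carries half the distortion of the first, but not zero.

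**5. A complier-average effect as an alternative.** With 56 v 28 followed up, the ITT SE is 1.307 (A) or 1.250 (B). Dividing by the 50% completion proportion gives 2.61 or 2.50, and power for a 4-point effect of about 33% or 36% (normal).

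**The case against.** The best defence is that 3.3.2 is unclear rather than contradictory. Effect in this trial means dCBT-I against usual care, so the section could mean that the effect in completers and the effect in non-completers are each taken against controls. On that reading it agrees with 2.3. This is possible, but it is not written. A further reading, in which controls count among those with fewer than four modules, would pool them with non-completers, and 2.3 did not size that either. Several admissible readings of one pre-specified analysis are themselves the defect.

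The section also says the analysis is meant to explore, and nothing confirmatory rests on it. That is true and limits the severity. Yet 2.3 lets this same analysis set the recruitment target.

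Three points stand in full:

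- Section 2.3 does not state completers versus controls as a hypothesis. That is inferred from the counts and the power, using ITT inputs that the SAP does not say apply to completers.
- The bias figures depend on an assumed correlation and an assumed model. If r were the correlation with the yes/no completion variable at a 50/50 split, the difference would be 2 × r × 4 = 0.8–3.2 points. They show direction and scale and should not drive the severity.
- Completers versus controls is not free of selection. Naming the control arm cures the inconsistency, not all of the bias.

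**Conclusion.** The concern holds and should be fixed. SAP 2.3 and 3.3.2 do not state the same per-protocol comparison, and no later section reconciles them. The figures support completers versus controls as the contrast behind 21 clusters: 78–84% power at 21 against 61–71% at 15, across both formulas and both reference distributions. This assumes that the 4 points, SD 4, ICC 0.2 and CV 0.7 carry over to the per-protocol set. The contrast that 3.3.2 naturally describes is self-selected and cannot be read as an effect of dCBT-I; how far it would mislead is unknown. The ITT analyses of primary and secondary outcomes are untouched, so this is a moderate correction.

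**What to change.** The essential change is to rewrite SAP 3.3.2 so that it:

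- defines the per-protocol comparison as completers of at least four modules versus the control arm, on ISI at 3 months, in line with the counts in 2.3;
- states that randomisation does not protect this comparison;
- labels any comparison of ≥4 with <4 modules as descriptive only.

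The model should be specified at the same time. Adjust for the covariates of the primary model (age, sex, education), baseline ISI, and a short list of baseline predictors of completion from Table 1, such as HSCL-25, pain intensity and fatigue, fixed before unblinding. Include rehabilitation group as a random effect with small-sample degrees of freedom, since the sizing in 2.3 assumes an ICC of 0.2. A complier-average effect with randomised arm as instrument may be added as a supporting analysis, stating its assumption that fewer than four modules have no effect.

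The cost is SAP wording and one model specification, with no new data. SAP 5.2 already foresees an updated version before unblinding, and SAP 3.4.2 foresees published syntax, so both can carry the change. The limits should be stated: some selection bias remains after adjustment, about 28 completers allow only a few covariates, and the complier estimate (SE about 2.5–2.6, power about 33–36%) cannot carry the per-protocol conclusion.
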